## **Patient Selection**

Healthy adult volunteers eligible for participations in the study will be enrolled as study participants. They will be randomly assigned to the IMP NIPRIMUNE and placebo arm of the SAD/MAD part.

### **Inclusion/Exclusion Criteria**

#### Inclusion Criteria:

i. Age: Healthy adult volunteers between 18 and 55 years old.

- ii. Health Status: Normal vital signs and laboratory parameters, with no significant medical history.
- iii. Informed Consent: Ability to understand and sign the informed consent form.
- iv. Reproductive Status: Women of childbearing potential must have a negative pregnancy test and agree to use effective contraception.

#### Exclusion Criteria:

- i. Medical Conditions: Presence of significant medical conditions, such as liver or kidney disease, heart conditions, or neurological disorders.
  - a. AST and/or ALT >3x upper limit of normal or any sign of hepatic impairment limit of normal or any other significant renal or hepatic impairment.
  - b. QTc interval of >470 msec at screening and patients with congenital long QT syndrome/or creatinine >2x renal dysfunction.
- ii. Medications: Use of medications that may interact with NIPRIMUNE or affect the study outcomes.
- iii. Lifestyle Habits: Smoking, alcohol or drug abuse, or extreme diets and exercise routines.
- iv. Pregnancy or Lactation: Pregnant or breastfeeding women.
- v. Allergies: Known hypersensitivity to Andrographis paniculata or similar herbal products

## Study Site: NIPRD Research Clinic IDU

**Study Population:** Fifty six healthy participants will recruited from our pool of clients and from the eleven communities located around the institute.

## **Study Design**

**Interventional Model Description:** Phase I, Randomized, Double-blind, Placebo-controlled, Single Ascending Dose and Multiple Ascending Dose Clinical Study to Assess the Safety, Tolerability and Pharmacokinetics of the Investigational Product in Healthy Adult Volunteers

Both the Investigator and study participants will remain blinded to the treatment administered (drug or placebo) till the final results of the study are obtained.

The placebo will identical to the investigational medicinal product in smell, taste, and appearance.

#### **Arms and Interventions**

Participant Group/Arm	Intervention/Treatment
Experimental: NIPRIMUNE is a phytomedicine that has demonstrated positive outcomes during in vitro and in vivo studies for immune	NIPRIMUNE is a small molecule with demonstrated antiviral and immunomodulatory activity in-vitro & in

Participant Group/Arm	Intervention/Treatment
booster with antiviral charactreristics	vivo studies., it was anticipated that NIPRIMUNE can also be a promising immune booster
Formulated as Capsules intended for oral dosing to trial participants.	
Placebo Comparator: Placebo  placebo will be identical in smell, taste, and appearance to the Capsule of NIPRIMUNE	Placebo capsules identical in appearance, taste and smell to the capsules of NIPRIMUNE

This clinical study is planned as a double blind, randomised, placebo-controlled, combined clinical study of two parts: Single Ascending Dose (SAD) and Multiple Ascending Dose (MAD) studies, respectively. Pharmacokinetic (PK) profile of the NIPRIMUNE, will also be assessed in both parts of the study. The safety, tolerability and pharmacokinetic data and results obtained from this study will determine the potentially efficacious doses of the IMP NIPRIMUNE, in the subsequent efficacy studies.

Fifty six (56) healthy volunteers will be recruited age for sex. Randomised, The SAD Part will consist of 5 cohorts of 8 healthy adult volunteers, each volunteer will be randomly (blinded) allocated to NIPRIMUNE or placebo (each cohort will consist of 6 volunteers receiving NIPRIMUNE and 2 volunteers receiving placebo). Five (5) dose level of the investigational medicinal product are selected for oral administration. The MAD Part will consist of 2 cohorts of 8 healthy adult volunteers, each volunteer will be randomly (blinded) allocated to NIPRIMUNE or placebo (each cohort will consist of 6 volunteers receiving NIPRIMUNE and 2 volunteers receiving placebo). Two (2) dose levels of the investigational medicinal product are selected for oral administration. Additional Volunteers will be enrolled to replace(volunteers withdrawing consent from the study for reasons other than safety). Additional volunteers will also be enrolled if a Cohort needs to be repeated.

Safety evaluation during both the SAD & MAD pars of the clinical study will include adverse events, clinical laboratory/ pathological test results, electrocardiogram (ECG), and measurement of vital signs.

Pharmacokinetics will be determined at pre-dose, and 30 min, 1h, 2h, 4h, 8h, 12h, and 24, post-dose, and 36 hrs post-dose on Day 2, for the SAD Part of the Study.

Pharmacokinetics will be determined at pre-dose, and 30 min, 1h, 2h, 4h, 8h, 12h, and 24h, of Day 1 and Day 7, at pre-dose on Days 2-6 and 36 hrs post final dose of Day 7 for the MAD Part

Safety analysis: frequency and severity of adverse events. The sample size is estimated to produce a good clinical effect at a 95% confidence and a power of 90. The participants will be randomized into two groups labeled A and B.

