## **Hypothesis:**

## Null Hypothesis:

Industrial-scale production of NIPRIMUNE granules using a cGMP-compliant facility and phase 1 clinical trial will not significantly improve the quality, safety, and effectiveness of NIPRIMUNE, nor its market acceptability and penetration.

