## Some benefits of the NIPRIMUNE project:

- 1. Improved healthcare outcomes and overall well-being for Nigerians by preventing and treating diseases through enhanced immune systems.
- 2. Easy access to NIPRIMUNE as a standardized herbal product with proven efficacy and safety.
- 3. Creation of employment opportunities, thus boosting Nigeria's economic growth.
- 5. Advancement of research and development in the herbal pharmaceutical industry.
- 6. Development of standardized production and quality control processes and protocols.
- 7. Generation of valuable safety and efficacy data through Phase 1 clinical trials that will confer confidence in its integration into mainstream healthcare system.

- 8. Boosting the phyto-pharmaceutical industry's growth.
- 9. Increase in the acceptability and competitiveness of Nigerian herbal products globally.

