## **Response Outcome Measures**

## Current Primary Outcome Measures:

Determine the safety, tolerability, and dose-limiting toxicities of medication. Determine the safety, tolerability, and dose limiting toxicities of NIPRIMUNE Assessed by frequency and severity of adverse events(AEs), and changes in vital signs, 12-lead ECGs and laboratory assessments as compared to baseline [Time Frame: From the time the participant is administered the first dose through the final follow up clinic visit, for a total of 12weeks

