## Primary outcome measures

Outcome Measure	Measure Description	Time Frame
Number of participants with adverse events [Time Frame-]	To assess safety & tolerability of NIPRIMUNE in Human	30 days post last dose for each cohort
Incidence of serious adverse events (SAEs) by relation to the IMP (related/not related)	To assess safety & tolerability of NIPRIMUNE in Human	30 days post last dose for each cohort
Percentage of volunteers who experience at least 1 Treatment Emergent Adverse Event (TEAE)	To assess safety & tolerability of NIPRIMUNE in Human	30 days post last dose for each cohort
Percentage of volunteers who discontinue due to an Adverse Event (AE).	To assess safety & tolerability of NIPRIMUNE n Human	30 days post last dose for each cohort
Percentage of volunteers who meet the markedly abnormal criteria for safety laboratory tests at least once post dose.	To assess safety NIPRIMUNE in Human	7 days post last dose for each cohort

Outcome Measure	Measure Description	Time Frame
Percentage of volunteers who meet the markedly abnormal criteria for vital sign measurements at least once post dose	To assess safety NIPRIMUNE in Human	7 days post last dose for each cohort
Percentage of volunteers who meet the markedly abnormal criteria for safety electrocardiogram (ECG) parameters at least once post dose.	To assess safety NIPRIMUNE in Human	7 days post last dose for each cohort

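### The claim of 95% confidence and 90% power is tied to no endpoint, effect or test, and one 6:2 cohort essentially cannot deliver it for adverse events

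*Protocol*

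**What the plan says.** The Protocol makes the claim twice, under Arms and Interventions and under DATA ANALYSIS: "The sample size is estimated to produce a good clinical effect at a 95% confidence and a power of 90". In both places it goes on to say that participants are randomised to two groups, A and B.

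Arms and Interventions gives the layout: five single-dose (SAD) cohorts and two multiple-dose (MAD) cohorts of eight, 56 in all, where "each cohort will consist of 6 volunteers receiving NIPRIMUNE and 2 volunteers receiving placebo".

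The primary outcomes are safety measures. They include "changes in vital signs, 12-lead ECGs and laboratory assessments as compared to baseline" and binary outcomes such as "Percentage of volunteers who experience at least 1 Treatment Emergent Adverse Event (TEAE". The Secondary Outcome Measures table is all pharmacokinetics. DATA ANALYSIS describes safety by frequency and severity of adverse events, and names inferential methods only for dose-proportionality and pharmacokinetic parameters.

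**The concern.** A power figure means something only for a named comparison, effect and test. Here the target is "estimated to produce a good clinical effect", with no outcome attached and no size given. Immune and inflammatory markers are collected, but they appear in neither outcome table and no effect on them is specified. The total equals the number of cohorts times the cohort size.

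At stake is how the results will be read. Someone who takes the 90% at face value would expect the trial to be able to settle a drug-against-placebo question, and could read similar adverse-event counts in the two arms as informative. With six active and two placebo volunteers per dose, they carry little information. The claim is a stated property of a size that the protocol has already fixed, so it is not a detail left to a later analysis plan.

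**Working it through.** **Inputs from the protocol.** Confidence 95%, read as alpha 0.05; sidedness is not stated and two-sided is used here. Power 90%. SAD 5 × 8 = 40 and MAD 2 × 8 = 16, total 56. At 6:2 per cohort, active is 7 × 6 = 42 and placebo 7 × 2 = 14.

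**Not in the protocol.** Effect size, event rates, SDs and test. The placebo rates below are my assumptions, shown as a range.

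**Reproducing the 90%.** This is not possible, because the inputs are missing. The check therefore runs backwards: what effect would give 90% power?

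**One cohort, 6 against 2, Fisher exact.** In the direction of harm the only significant table is 6/6 against 0/2, with p = 1/C(8,2) = 1/28 = 0.036. Power against harm is therefore p₁⁶ × (1 − p₀)², where p₁ is the active rate and p₀ the placebo rate; the mirror table adds nothing material here.
- p₀ = 0%: 90% power needs p₁ = 0.90^(1/6) = 0.983, about 98%.
- p₀ = 5%: even p₁ = 100% gives only 0.95² = 90.25%.
- p₀ = 10%: the maximum is 0.90² = 81%.
- p₀ = 20%: the maximum is 0.80² = 64%.

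**All cohorts pooled, 42 against 14, Fisher exact by enumeration.**

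| Placebo | Active | Power |
|---|---|---|
| 0% | 35% | 92% (34% gives 89%) |
| 10% | 57% | 90% |
| 20% | 71% | 90% |
| 30% | 80% | 90% |
| 10% | 30% | 27% |
| 20% | 40% | 22% |

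Over placebo rates of 0% to 30%, 90% power thus needs a difference of roughly 35 to 51 percentage points.

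**Continuous measure, two-sample t test.** Noncentrality is d × √(n₁n₀/(n₁ + n₀)). For 42 against 14 this is d × √10.5, and 90% power needs d = 1.02 SD. For 6 against 2 it needs d = 3.2 SD.

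**Equal groups A and B, 28 against 28.** This split contradicts the 6:2 allocation but is one way to read the sentence about two groups. It needs 0.88 SD. Power is 33% for 10% against 30% and 28% for 20% against 40%.

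**What the cohort size does give.** The chance of at least one event is 1 − (1 − p)ⁿ, and the one-sided 95% upper limit after no events is 1 − 0.05^(1/n).
- n = 6: 1 − 0.9⁶ = 47% at a true rate of 10%. A 90% chance needs a rate of 1 − 0.1^(1/6) = 32%. After 0/6 the upper limit is 39%.
- n = 42: after 0/42 the upper limit is 6.9%, but only if one event rate holds across all doses and across SAD and MAD.

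**The case against.** A reader might infer that the design has 90% power for no plausible safety effect. The documents do not support that. They give no rates or SDs by which to call an effect implausible, and large effects do reach 90% when the cohorts are pooled: 0% against about 35%, or about 1 SD. The primary outcome also covers change from baseline. A within-participant change in all 42 active volunteers reaches 90% power at about 0.51 SD (paired t, two-sided 5%). It too requires pooling across doses, but it is a moderate effect. This objection stands, and the point is limited accordingly.

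A reader might also conclude that 56 was never calculated. That is only an inference from 7 × 8 = 56. A 3:1 calculation at 1.02 SD also gives 56 by the normal approximation, but no such effect appears in the protocol.

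The harm should not be overstated. The protocol names no between-arm test of safety, and the Introduction to the trial section bases escalation on the monitoring board's review of pharmacokinetic and safety data, not on a powered test. This also stands.

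Finally, the stated null hypothesis, "Industrial-scale production of NIPRIMUNE granules using a cGMP-compliant facility and phase 1 clinical trial will not significantly improve the quality, safety, and effectiveness", is not a drug-against-placebo contrast, and the project section promises "Generation of valuable safety and efficacy data through Phase 1 clinical trials". It is tempting to demand that both be rewritten. They belong to the manufacturing and funding part of the document. The trial section states a safety, tolerability and pharmacokinetic purpose and defers efficacy to later studies, so correcting the power claim does not require rewriting them.

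None of this supplies the missing endpoint, effect and test.

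**Conclusion.** The concern holds in limited form. The statement "at a 95% confidence and a power of 90" is a design claim that the protocol does not support and that cannot be reproduced. For a between-arm adverse-event comparison, 90% power is essentially unreachable within one 6:2 cohort. Pooled over 42 and 14, an analysis the protocol does not describe, it would need about 0% against 35%, 10% against 57% or 20% against 71%, or about 1.0 SD on a continuous measure.

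These figures rest on a two-sided 5% level, the Fisher exact or two-sample t test, and assumed placebo rates. The pooled figures also assume one common active rate or mean across doses and across SAD and MAD. The defect is an unsupported claim, not a demonstrated miscalculation. It does not show that the cohort sizes are unsuitable for an ascending-dose safety study.

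**What to change.** Delete the power sentence under both Arms and Interventions and DATA ANALYSIS. State instead that the size follows the SAD/MAD cohort layout (5 × 8 + 2 × 8, with 6 active and 2 placebo in each), and give its precision. Six active volunteers per cohort have a 47% chance of showing at least one event at a true rate of 10%, and a 90% chance at 32%; 0/6 excludes rates above 39% (one-sided 95%). Give a pooled figure, such as 0/42 excluding rates above 6.9%, only together with the stated assumption of a common event rate across doses and across SAD and MAD.

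If the sponsor wants to keep a power claim, the alternative is to name the endpoint, effect, test and pooling that produce 90%.

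The cost is wording only. Enrolment does not change, and the stated figure becomes less favourable.

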## **Study Procedure**

**Study Procedures:** An appropriate health diary has been designed which will be completed daily by each participant for one month prior to the administration of the NIPRIMUNE. The participants are also expected to continue to complete the health diary for the duration of the clinical evaluation, which will last for 12 weeks

The purpose of this study is to determine the dose tolerability and safety of NIPRIMUNE when given to normal healthy participants. Pre-dose blood sampling will be done at zero (0) minute, and post-administration of NIPRIMUNE or Placebo at pre-dose, and 30 min, 1h, 2h, 4h, 8h, 12h, and 24, post-dose, and 36 h. post-dose on Day 2, for the SAD Part of the Study.

Pharmacokinetics will be determined at pre-dose, and 30 min, 1h, 2h, 4h, 8h, 12h, and 24h, of Day 1 and Day 7, at pre-dose on Days 2-6 and 36 h post final dose of Day 7 for the MAD Part

The participants will be followed up 24 h, 72 h, one week, and then weekly during the first 4 weeks and subsequently at the end of every 4 weeks for 8 weeks.

During each visit, they will be physically examined, and any side effects and adverse events will be recorded. At the end of 12 weeks, the following investigations taken at baseline will be repeated: urinalysis, urea and creatinine, random blood sugar, full blood count and differentials, serum electrolytes, liver function tests, immunomodulator and anti inflammatory markers, ECG, and chest X-ray.

*Pre – Entry Tests:* Within seven days prior to dosing and as close to the first day of dosing as possible, the following tests must be performed to determine patient eligibility and baseline values:

\*Medical history, Complete physical examination, \*Weight, height

\*Vitals signs\*ECG; Chest X-ray

\*Complete haematology WBC, differential, HCT, Hgb, platelets, I

\*Blood chemistry (Na, K, Cl, CO2, BUN, Creatinine, albumin, alkaline phosphatese,LDH, ALT,AST, bilirubin total and direct, hepatitis panel, glucose, cholesterol, serum iron). C – reactive protein ,ESR

Immune modulator markers CD4+, T cells ,CD8 + T cells IL-2, IL-6, IL-10, TNF- $\alpha$ , IFN- $\gamma$ , IL-17, CXCL9, CXCL10

\*Urinalysis (pH, gram strain, colour, glucose, cells, protein, specific gravity).

\*Ova and parasites

\*TB test (if the patient did not receive BCG)

\*On day 1, immediately prior to beginning dosing, repeat measurement of vital signs.

\*At any reasonable time before entry (i.e more than 7 days if necessary) determine HIV positivity.

\*If the patient is female, confirm that she is not pregnant and is practicing appropriate contraception.

## Test During Study, Recording

DAY 1, until the end of treatment course (see schedule of visits)

- \*Vital signs: Immediately pre-treatment and after the dose at 2 and 4 hours.
- \*Weight, Height and Vital Signs are to be taken at each visit.
- \*Stool Microscopy is to be done pre-trial and after the clinical evaluation.
- \* A repeat ECG is to be taken within the first 4 weeks.
- \*Haematology: Complete haematology including reticulocytes; pretreatment and at each visit.
- \*Blood chemistry: Na, Ca, K, Cl, CO2, BUN, Creatinine, albumin, total protein, alkaline phosphatese, LDH, ALT, AST, bilirubin total and direct, , glucose, cholesterol, pretreatment and at each visit

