One of the significant challenges in the production of herbal medicines is standardization, particularly in relation to extraction, formulation, and quality control protocols, as well as corroborating folk safety and efficacy claims. To address this challenge, our proposed research and development project aims to strengthen the NIPRD's facility for producing granules of water extracts from various medicinal plants, with NIPRIMUNE® serving as a prototype. We will utilize innovative optimized procedures and technology to ensure the production of high-quality herbal products.

NIPRIMUNE® is a phytomedicine developed by NIPRD through meticulous research and development efforts. It is derived from *Andrographis paniculata* and has been standardized and formulated using innovative techniques. NIPRIMUNE® is registered under the trademark and listed with NAFDAC, ensuring its authenticity and quality. This herbal medicine is designed as an immune booster that alleviates several health conditions, including antiviral, antibacterial, flu-like symptoms, diarrhea, fevers, inflammation, and high blood pressure, thereby promoting general well-being.

The goal of this project is to effect commercial production of NIPRIMUNE by upgrading NIPRD's drug manufacturing facility to a cGMP-compliant phyto-medicine factory and conduct Phase 1clinical trial to establish the clinical safety of the product.

The commercial development of NIPRIMUNE aligns ultimately with the Renewed Hope Agenda of [name] as well as the working objective NASENI as far as innovative research and development, entrepreneurship, sustainable healthcare options and wealth creation.

Funding this project will unlock the full potential of Nigeria's biodiversity and break the ice for sustainable healthcare and economic growth. We believe that this project will make a significant contribution to the development of the herbal medicine industry in Nigeria and improve the health and well-being of Nigerians. It is sure to offer a bright future and opportunity for innovation, entrepreneurship, and collaboration in Nigeria.

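### Between dosing and the 24 h visit, vital signs are timed only at 2 h and 4 h while PK is also drawn at 0.5, 1, 8 and 12 h, so the primary vital-sign outcome can miss a transient change

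*Protocol*

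**What the plan says.** Under Test During Study, Recording, the protocol times vital signs during treatment as "Immediately pre-treatment and after the dose at 2 and 4 hours". The next item adds that "Weight, Height and Vital Signs are to be taken at each visit". Visits are set under Study Procedure: "The participants will be followed up 24 h, 72 h, one week, and then weekly during the first 4 weeks", then every 4 weeks for 8 weeks. The first reading after 4 h is therefore at 24 h.

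PK sampling is denser. For the SAD part, Arms and Interventions states: "Pharmacokinetics will be determined at pre-dose, and 30 min, 1h, 2h, 4h, 8h, 12h, and 24, post-dose, and 36 hrs post-dose on Day 2". The MAD part uses the same grid, "30 min, 1h, 2h, 4h, 8h, 12h, and 24h, of Day 1 and Day 7", with pre-dose samples on the days between and a 36 h sample after the last dose.

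One of the primary outcomes is "Percentage of volunteers who meet the markedly abnormal criteria for vital sign measurements at least once post dose", with a time frame of 7 days after the last dose. The narrative primary outcome also includes change in vital signs from baseline. The Introduction to the clinical trial section makes escalation to the next cohort depend on interim PK and safety data reviewed by the DSMB.

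**The concern.** An outcome that counts a volunteer once any post-dose reading is abnormal depends on when readings are taken. Intervals without a reading can lower the count but never raise it. The text leaves two such intervals on the dosing day, 0-2 h and 4-24 h. Participants already have blood drawn twice in each of them (0.5 and 1 h; 8 and 12 h).

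Three things make this worth attention. The outcome is primary and contributes to escalation decisions. Each cohort has only 6 participants on active product, so one missed participant is 1/6, or about 17%, of the active group. And vital signs cannot be set against concentration at the unpaired draws, although the plan pays for those concentrations. A cardiovascular effect is not far-fetched on the protocol's own account, since Background lists "flu-like symptoms, diarrhea, fevers, inflammation, and high blood pressure" among the conditions the product is said to relieve.

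**Working it through.** The plan states no figure on this point, so there is none to reproduce. The check compares the two time grids and then illustrates what the early gap could mean.

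**1. Time grids, SAD part**

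| Post-dose time (h) | 0.5 | 1 | 2 | 4 | 8 | 12 | 24 | 36 |
|---|---|---|---|---|---|---|---|---|
| PK draw | yes | yes | yes | yes | yes | yes | yes | yes |
| Vital signs | no | no | yes | yes | no | no | yes (visit) | no |

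Of the 6 draws in the first 12 h, 2 have a paired reading. The same comparison holds for the 0.5-24 h profiles on MAD Days 1 and 7.

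**2. Concentration at the 2 h reading (illustration)**

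The protocol gives neither Tmax nor half-life; Tmax is itself a secondary outcome. Both are therefore assumed here. The model is one compartment with first-order absorption and elimination, suited to an oral capsule:

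- ke = ln 2 / half-life
- Tmax = ln(ka/ke) / (ka − ke), solved for ka
- C(t) is proportional to exp(−ke·t) − exp(−ka·t)

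Hand check, Tmax 1 h and half-life 1 h: ka = 2ke gives Tmax = ln 2 / ke = 1 h. Then C(1) ∝ 0.5 − 0.25 = 0.25 and C(2) ∝ 0.25 − 0.0625 = 0.1875. The ratio is 0.1875 / 0.25 = 75%.

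Concentration at 2 h as a percentage of peak:

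| Assumed Tmax | Half-life 1 h | 2 h | 4 h | 7 h |
|---|---|---|---|---|
| 0.5 h | 42 | 63 | 79 | 87 |
| 1 h | 75 | 82 | 89 | 93 |
| 1.5 h | 96 | 96 | 97 | 98 |
| 2 h | 100 | 100 | 100 | 100 |
| 3 h | 94 | 93 | 94 | 95 |

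With Tmax 3 h, the 4 h reading is at 96-97% of peak. The 2 h reading falls clearly short of peak only if Tmax is about 1 h or less, and most of all with a short half-life. The table does not address a change arising between 4 h and 24 h; that gap follows from the time grids alone.

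**3. Effect of extra readings on chance findings**

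In the SAD part, the visible post-dose readings within 7 days are at 2, 4, 24 and 72 h and one week, which is 5. Adding 0.5, 1, 8 and 12 h makes 9. Assume each reading has an independent 1% chance of being markedly abnormal without any drug effect:

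- 5 readings: 1 − 0.99^5 = 4.9%
- 9 readings: 1 − 0.99^9 = 8.6%

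Among 6 active participants, the expected number flagged by chance goes from 6 × 0.049 = 0.29 to 6 × 0.086 = 0.52 per cohort.

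**The case against.** The strongest reply is that this is a sparse schedule, not an error, and that the harm is hypothetical. Much of that stands.

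- Vital signs are not limited to 2 h and 4 h over the whole study. Readings at the 24 h, 72 h and one-week visits fall within the 7-day window and can count. They do not close either dosing-day gap.
- A reader might infer from the 30 min sample that the sponsor expects a peak that early. The protocol lists times without reasons, and early samples are needed to describe the rising part of any oral curve.
- A reader might also infer that the sponsor expects blood pressure to fall in these volunteers. Background makes a general claim about high blood pressure. It says nothing about people enrolled with normal vital signs and gives no time course.
- Simple exponential decline from the peak would suggest a larger shortfall, such as 50% of peak at 2 h for Tmax 1 h and half-life 1 h. That ignores continuing absorption from a capsule; the figure is 75%.
- If Tmax is 1.5 to 3 h, the existing readings lie near the peak. An effect on blood pressure may also lag concentration.
- The DSMB sees adverse events, laboratory tests, ECG and PK as well, and participants keep a daily diary. A symptomatic fall in blood pressure should surface as an adverse event. What would be lost is mainly a transient change without symptoms.
- The text points to a separate schedule of visits that is not shown and may list further times. The wording at hand is nevertheless explicit about 2 h and 4 h.

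**Conclusion.** The point holds as a cheap improvement to the assessment schedule. As written, no vital signs are timed in 0-2 h or 4-24 h after dosing, although four PK draws fall there. The primary vital-sign outcome can therefore only undercount changes confined to those intervals.

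How much is missed cannot be established from the protocol. On assumed half-lives of 1 to 4 h, the 2 h reading sees 42-79% of peak concentration if Tmax is 0.5 h, 75-89% if it is 1 h, and 93-100% if it is 1.5 to 3 h. These figures describe concentration; they carry over to effect only if effect follows concentration closely. The documents do not support the stronger conclusion that the schedule will miss a peak effect, or that dose levels will be judged safer than they are.

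**What to change.** In Test During Study, Recording, align the vital-sign times with the existing PK draws on full-profile days (SAD Day 1, MAD Days 1 and 7). Add a reading just before each draw that has none (0.5, 1, 8 and 12 h), keep the present 2 h and 4 h readings, and leave other days unchanged. State under Primary outcome measures that the added readings count towards the vital-sign outcome, and make the schedule of visits agree. No dose, treatment or stopping rule changes.

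The cost is one protocol line and a few minutes at contacts that already take place. The downside is the higher chance of an isolated abnormal value shown above (4.9% to 8.6% under the assumed 1% per reading). It applies to both arms, so the percentages should be read against placebo. With 2 placebo participants per cohort and 14 overall (7 × 2), that comparison is coarse within a cohort.

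### The primary ECG outcome closes 7 days after the last dose, but the written schedule does not guarantee any post-dose ECG inside that window

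*Protocol*

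**What the plan says.** The table under Primary outcome measures in the Protocol lists "Percentage of volunteers who meet the markedly abnormal criteria for safety electrocardiogram (ECG) parameters at least once post dose", with the time frame "7 days post last dose for each cohort".

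The text schedules three ECGs:

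- **Before entry** (Study Procedure): ECG is among the baseline tests. "Within seven days prior to dosing and as close to the first day of dosing as possible, the following tests must be performed".
- **Repeat** (Test During Study, Recording): "A repeat ECG is to be taken within the first 4 weeks".
- **End of study** (Study Procedure): "At the end of 12 weeks, the following investigations taken at baseline will be repeated"; ECG is in the list that follows.

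On visits, Study Procedure states: "The participants will be followed up 24 h, 72 h, one week, and then weekly during the first 4 weeks". Other safety measures are tied to dosing or to these visits. For vital signs the rule is "Vital signs: Immediately pre-treatment and after the dose at 2 and 4 hours", and they are also taken at every visit. For blood counts it is "Complete haematology including reticulocytes; pretreatment and at each visit", and chemistry follows the same pattern.

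Arms and Interventions names ECG as a safety evaluation in both the single ascending dose (SAD) and multiple ascending dose (MAD) parts, but gives no times. Response Outcome Measures gives a second primary statement: change from baseline in 12-lead ECGs, from first dose to the final visit at 12 weeks.

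**The concern.** The outcome can be measured only if an ECG is taken after dosing and before the window closes. The pre-entry ECG comes too early and the 12-week ECG too late, so the outcome rests on one recording whose permitted period runs well past the window. Nothing in the text links that recording to drug exposure or to the outcome it has to supply.

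With six active participants per cohort, the loss of a few ECGs matters. If a participant without an in-window ECG is counted as not abnormal, the reported percentage is biased downward, toward apparent safety. If such participants are excluded, the estimate loses precision. The DSMB, which rules on each escalation, could also do so without an ECG taken near exposure. An analysis plan can choose the denominator, but it cannot recover an ECG that was never recorded.

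**Working it through.** The plan gives no figure for ECG coverage, so there is none to reproduce. The check compares the outcome window with the permitted timing.

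**Inputs**

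- SAD: 5 cohorts × 8 = 40 participants. MAD: 2 cohorts × 8 = 16. Total 56, as stated (Arms and Interventions).
- Last dose: the single dose in SAD; Day 7 in MAD, which is 6 days after first dose.
- Window: taken generously as any time from first dose to 7 days after last dose.
- Visits in the first four weeks: 24 h, 72 h, and weeks 1, 2, 3 and 4, so six visits (Study Procedure).
- Repeat ECG: any of the first 28 days. The text does not say whether these run from first or last dose.

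**Where the window closes**

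- SAD: day 0 + 7 = day 7. Visits at 24 h, 72 h and week 1 are inside; weeks 2, 3 and 4 are outside. That is 3 of 6 visits, or 7/28 = 25% of permitted days.
- MAD: 6 + 7 = 13 days after first dose. The same three visits are inside, and the week-2 visit at day 14 is outside. That is 3 of 6 visits, and 13/28 = 46% of permitted days if the 28 days run from first dose, or 7/28 = 25% if from last dose.
- The ECG at 12 weeks (day 84) is outside in both parts.

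**Bounds needing no assumption**

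If every repeat is booked by the week-1 visit, 0 of 56 participants lack an in-window ECG. If every repeat is booked at week 4, 56 of 56 do. Both comply with the text.

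**Illustrations under assumed booking patterns**

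| Assumed timing of the repeat | SAD in window | SAD without | MAD without | Total without |
|---|---|---|---|---|
| Even over the six visits | 50% | 40 × 0.50 = 20 | 16 × 0.50 = 8 | 28 of 56 |
| Even over 28 days from first dose | 25% | 40 × 0.75 = 30 | 16 × 15/28 = 8.6 | about 39 of 56 |
| Even over 28 days from last dose | 25% | 40 × 0.75 = 30 | 16 × 0.75 = 12 | 42 of 56 |
| All at week 4 | 0% | 40 | 16 | 56 of 56 |

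**Comparison with other measures**

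Vital signs, haematology and chemistry are required at every visit. The 24 h, 72 h and one-week visits therefore supply their 7-day windows; the ECG has no such rule. Urinalysis is scheduled only before entry and at 12 weeks, so on the written schedule none falls within 7 days of the last dose.

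**The case against.** **The schedule of visits may fix the ECG day.** Test During Study, Recording refers to it, and Data Collection Forms lists it beside a cardiac form; neither is shown. That section also runs its tests only to the end of treatment, which pulls against a late ECG. This is fair, but the ECG line itself allows four weeks, far longer than one day of dosing in SAD or seven in MAD. The wording needs correcting whatever the form says.

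**The 12-week primary statement is served.** The later ECGs do supply the outcome in Response Outcome Measures. They do not supply the 7-day outcome, and the two time frames themselves need reconciling.

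Four stronger readings are tempting but are not supported:

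- *Three quarters of SAD participants will be missed.* That assumes bookings spread evenly over days, but participants attend at discrete visits. The choice matters: the chance that none of six active participants in a SAD cohort has an in-window ECG is 0.75^6 = 18% on the day model and 0.5^6 = 1.6% on the visit model. Both assume independent bookings, which is doubtful at a single named site.
- *The DSMB will escalate without ECG data.* The trial's Introduction also bases escalation on 30-day safety follow-up. In SAD, a repeat taken within 28 days precedes that point, so the DSMB should have a post-dose ECG, though possibly not one near exposure.
- *Any missing ECG biases the result toward safety.* Only counting it as not abnormal does so. Exclusion has no stated direction of bias.
- *Urinalysis has the same fault.* The general list of trial parameters includes it as a laboratory test, but the primary outcome table does not say which tests it covers. Haematology and chemistry do supply that outcome with data.

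**Conclusion.** The point holds as a mismatch between a primary outcome and the schedule meant to supply it. The firm statement is that full compliance can leave from 0 to 56 of 56 participants without an ECG in the 7-day window. The intermediate figures of 28 to 42 depend on assumed booking patterns and only illustrate the range. The conclusion is the same whether the four weeks run from first or last dose. It rests on the protocol text alone and would be softened, though not removed, if the schedule of visits fixed an earlier ECG. Whether urinalysis belongs to the 7-day laboratory outcome is a secondary question of clarity.

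**What to change.** Reconcile Study Procedure, Test During Study, Recording, both statements of the primary outcome and the schedule of visits, and settle the 7-day against the 12-week time frame at the same time.

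- Place the already planned repeat ECG at an existing attendance inside the outcome window, no later than one week after the last dose, in both SAD and MAD. The protocol gives no expected time of peak concentration, so it does not support one particular hour; any attendance inside the window removes the contradiction.
- Base the ECG percentage on participants with at least one post-dose ECG in the window, and report how many had none.
- State whether urinalysis is part of the 7-day laboratory outcome. If it is, align its timing with that window.

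**Cost:** an amendment of wording, with the same number of ECGs at visits already planned; a urinalysis may be added or moved. The drawback is that moving the single repeat leaves no scheduled ECG between that attendance and week 12. The sponsor should accept that gap knowingly when reconciling the sections.
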